### 9.3.3. Covariates

All members of the study cohorts will be described according to covariates identified in the claims data. Demographic attributes will be determined on the vaccination/cohort entry date, while other factors will be assessed in the one year prior to the cohort entry date. Unless specified as for descriptive purposes only, the covariates listed will be included in the PS models. All variables are binary unless otherwise specified.

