#### Comorbidities

- Asthma
- Non-malignant blood disorders, including sickle cell disease
- Chronic lung disease, including chronic obstructive pulmonary disease (COPD)
- Down syndrome
- Heart disease
- History of SARS-CoV-2 infection
- Immunocompromised status (i.e., history of human deficiency virus [HIV]; organ, bone marrow or stem cell transplant; use of immunosuppressant medication)
- Kidney disorders, including chronic kidney disease
- Liver disorders
- Neurological or neurodevelopmental conditions
- Malignant neoplasms
- Obesity
- Type 2 diabetes

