#### **Medication History**

- Systemic immunomodulators
- Oral corticosteroids
- Antivirals
- Antibiotics

In addition to the covariates listed above, baseline attributes will be identified on an empiric basis by examining the 25 most frequently occurring diagnoses, drugs dispensed, and procedures (including other baseline vaccinations, as captured through NDC and CPT codes) performed among individuals with and without COMIRNATY 2023-2024 Formula exposure.

These empiric covariates will be considered for inclusion in the PS models if they are potential confounders.

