#### 9.7.2. Cohort Study

##### 9.7.2.1. Propensity Score Modeling and Matching

The COMIRNATY 2023-2024 Formula-exposed and the unexposed comparator cohorts will be created as described in [Section 9.2.3](#). Each cohort member will be described with respect to baseline covariates as listed in [Section 9.3.3](#). These cohort members will be included in the propensity score modeling and matching.

This study will use a single PS model that encompasses risk factors for multiple outcomes, an approach demonstrated in other studies conducted to fulfill post-licensure regulatory commitments and requirements to the FDA and other regulatory agencies ([Seeger et al., 2023](#); [Ziyadeh et al., 2020](#)). While not all risk factors may be associated with all outcomes to the same degree, adjusting for covariates that are weakly or not at all associated with a given outcome is expected to result in negligible bias if residual confounding is small ([Brookhart et al., 2006](#); [Myers et al., 2011](#)). Incorporating a wide array of outcome predictors

(Section 9.3.3) into the PS is expected to minimize residual confounding, producing groups with similar patterns of both measured and unmeasured factors (Guertin et al., 2016).

The PS model will consist of a logistic regression model that incorporates the pre-specified demographic and comorbidity covariates, healthcare utilization, and calendar month of vaccination or cohort entry as independent variables, and an indicator for receipt of the COMIRNATY 2023-2024 Formula as the dependent variable. Two-way interactions of all variables with calendar month of vaccination or cohort entry, or empirically defined variables that are potential confounders, may also be considered for inclusion in the following model:

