$$\begin{aligned} & \text{logit}\{P(T_i = 1 \mid \mathbf{X}_i)\} \\ &= \beta_0 + \beta_1 \text{Sex (binary)}_i + \beta_2 \text{Age (categorical)}_i \\ &+ \beta_3 \text{Calendar month (categorical)}_i + \beta_4 \text{Geographic region (categorical)}_i \\ &+ \beta_5 \text{Asthma (binary)}_i + \beta_6 \text{Non-malignant blood disorders (binary)}_i \\ &+ \beta_7 \text{Chronic lung disease (binary)}_i + \beta_8 \text{Down syndrome (binary)}_i \\ &+ \beta_9 \text{Heart disease (binary)}_i \\ &+ \beta_{10} \text{History of SARS-CoV-2 infection (binary)}_i \\ &+ \beta_{11} \text{Immunocompromised status (binary)}_i \\ &+ \beta_{12} \text{Kidney disorders (binary)}_i + \beta_{13} \text{Liver disorders (binary)}_i \\ &+ \beta_{14} \text{Neurological or neurodevelopmental conditions (binary)}_i \\ &+ \beta_{15} \text{Malignant neoplasms (binary)}_i + \beta_{16} \text{Obesity (binary)}_i \\ &+ \beta_{17} \text{Type II diabetes (binary)}_i \\ &+ \beta_{18} \text{Number of hospitalizations in prior year (continuous)}_i \\ &+ \beta_{19} \text{Number of emergency room visits in prior year (continuous)}_i \\ &+ \beta_{20} \text{Number of outpatient encounters in prior year (continuous)}_i \\ &+ \beta_{21} \text{Seasonal influenza vaccination (binary)}_i \\ &+ \beta_{22} \text{RSV vaccination (binary)}_i + \beta_{23} \text{Systemic immunomodulators (binary)}_i \\ &+ \beta_{24} \text{Oral corticosteroids (binary)}_i + \beta_{25} \text{Antivirals (binary)}_i \\ &+ \beta_{26} \text{Antibiotics (binary)}_i + \beta_{27} \text{Identified empiric variables (binary)}_i, \end{aligned}$$

where  $T_i$  denotes exposure status for individual  $i$ , with  $T_i = 1$  indicating a recorded vaccination of the COMIRNATY 2023-2024 Formula and  $T_i = 0$  indicating no recorded vaccination of the COMIRNATY 2023-2024 Formula.

A greedy digit-based matching algorithm will be used, in which patients exposed to the COMIRNATY 2023-2024 Formula are matched without replacement to comparator patients at a given level of precision defined by the number of digits of the PS (Parsons, 2001), to a maximum of 8 decimal places. When no further matches are available at a given level of precision, the number of digits is sequentially reduced until a maximum allowable caliper of 0.1 is reached, thereby ensuring that the matched cohorts are comparable with respect to the underlying measured risk factors. Matching by propensity score will be conducted within

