strata defined by age group and calendar period. A matching ratio (e.g., up to 1:10) may be implemented.

PS matching will produce a single matched cohort (the master cohort) that will be used to conduct all primary, secondary, and sub-group analyses for the study outcomes. Balance between the PS-matched cohorts will be evaluated by overlaying graphs of the PS distributions in COMIRNATY-exposed and comparator cohorts before and after PS matching. Additionally, standardized differences between the PS-matched cohorts for each covariate in the model will also be assessed. Variables with an absolute standardized difference less than 0.1 will be considered balanced (Austin, 2009). If a variable has a standardized difference that is greater than 0.1, further PS model modifications (e.g., addition of interaction terms) or inclusion of the imbalanced covariates in an outcome model will be considered (Normand et al., 2001). If there are confounders identified that would only be appropriate to include for one outcome and not the others, a separate PS model for the specific outcome will be considered.

Outcome-specific exclusion criteria will be applied to the master cohort after PS matching but before the outcome specific analysis; the matched cohort that remains will be the analytic cohort for that specific outcome. The matched comparators of individuals excluded for outcome-specific exclusion criteria will also be excluded from the outcome-specific analysis.

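### Autoimmune disease is not a pre-specified propensity-score covariate in Phase 2 and is captured only indirectly, although at least seven of the 20 outcomes are immune-mediated

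*Protocol*

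**What the plan says.** Section 9.3.3 sets the rule for the PS: "Unless specified as for descriptive purposes only, the covariates listed will be included in the PS models". Thirteen comorbidities follow. The nearest to autoimmune disease is "Immunocompromised status (i.e., history of human deficiency virus [HIV]; organ, bone marrow or stem cell transplant; use of immunosuppressant medication". The medication list adds systemic immunomodulators and oral corticosteroids. The logistic model printed in Section 9.7.2.1 carries the same terms.

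The section then adds an empiric step: "baseline attributes will be identified on an empiric basis by examining the 25 most frequently occurring diagnoses, drugs dispensed, and procedures". Its result is discretionary: "These empiric covariates will be considered for inclusion in the PS models if they are potential confounders".

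Section 9.7.2.1 states the purpose of the model: "This study will use a single PS model that encompasses risk factors for multiple outcomes". On diagnostics it says that "standardized differences between the PS-matched cohorts for each covariate in the model will also be assessed", and that "Variables with an absolute standardized difference less than 0.1 will be considered balanced".

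Section 9.3.2 lists 20 safety outcomes. Section 9.9 makes the cohort study the primary analysis for chronic outcomes and gives multiple sclerosis (MS) as the example.

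**The concern.** Seven listed outcomes are immune-mediated on ordinary clinical classification: acute disseminated encephalomyelitis (ADEM), glomerulonephritis, Guillain-Barré syndrome, immune-mediated myositis, immune thrombocytopenia, MS and transverse myelitis. Existing autoimmune disease is a plausible shared risk factor for them, and may also be related to vaccine uptake. A single PS meant to cover risk factors for many outcomes would be expected to include it by name.

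Phase 1 is not affected in this way, because the self-controlled design removes time-fixed characteristics. Phase 2 relies on the PS. If autoimmune disease differs between the matched cohorts, the rate ratios for these outcomes can move away from 1 without a vaccine effect, or an effect can be masked. The planned diagnostics would not show this directly.

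The point cannot be left to a later analysis plan: Section 7 describes this document as the combined protocol and SAP, and the model is printed in it.

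**Working it through.** **Step 1: what the PS contains.**
- Named autoimmune terms among the 13 comorbidities, in the equation and in Appendix IV: none. The neurological covariate (17.4.1.10) covers F70 to F89 only, so it holds no neuro-immune codes.
- Treatment proxies: three, namely immunocompromised status, systemic immunomodulators and oral corticosteroids.
- Autoimmune diagnoses inside other groups: immune thrombocytopenia, Evans syndrome, autoimmune hemolytic anemia and antiphospholipid syndrome (17.4.1.2); glomerular disease, N00 to N08 (17.4.1.8); autoimmune hepatitis and primary biliary cirrhosis (17.4.1.9).

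**Step 2: how specific these are.**
- The immunomodulator term also covers chemotherapy, colony-stimulating factors and BCG.
- The steroid code list (17.4.2.2.1) includes injected, inhaled and intraocular products.
- The diagnoses sit with unspecified anemia, kidney stones and fatty liver respectively.
- Balance on such pooled binary terms does not ensure balance on autoimmune disease. A patient treated only with hydroxychloroquine or sulfasalazine, neither of which appears in 17.4.2.1, and with no code from the groups above, is invisible to all of them.

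**Step 3: possible size.** The protocol gives no prevalence, risk or imbalance on this point, so there is no planned figure to reproduce. All inputs below are assumptions. Let p0 and p1 be the prevalence of uncaptured disease in comparators and recipients, and R its risk ratio for the outcome.

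Bias factor = [1 + p1(R − 1)] / [1 + p0(R − 1)]

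Standardized difference (SMD) = (p1 − p0) / √{[p1(1 − p1) + p0(1 − p0)] / 2}

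| p0 | p1 | R | Bias factor | SMD |
|---|---|---|---|---|
| 3% | 3.3% | 2 | 1.003 | 0.017 |
| 5% | 6.25% | 5 | 1.042 | 0.054 |
| 8% | 12% | 5 | 1.121 | 0.134 |
| 5% | 7% | 5 | 1.28/1.20 = 1.07 | 0.08 |
| 5% | 7% | 10 | 1.63/1.45 = 1.12 | 0.08 |
| 5% | 10% | 5 | 1.40/1.20 = 1.17 | 0.19 |
| 5% | 10% | 10 | 1.90/1.45 = 1.31 | 0.19 |

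The first and third rows are the extremes of a grid with p0 from 3% to 8%, p1/p0 from 1.1 to 1.5 and R from 2 to 5. If comparators have more disease, the factors invert: 1/1.12 = 0.89 and 1/1.31 = 0.76.

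**Step 4: effect of the proxies.** Start from 5% against 7.5% and suppose that the existing terms remove 50% to 80% of the difference. Then p1 falls to between 6.25% and 5.5%. For R from 2 to 5 the bias factor is 1.012 to 1.042 at 50% removal, and 1.005 to 1.017 at 80%.

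**Step 5: what the 0.1 threshold would allow.** At p0 = 5%, an SMD of 0.1 corresponds to p1 = 7.4%, with a bias factor of 1.02 (R = 2) to 1.08 (R = 5). Passing the threshold therefore limits the bias but does not remove it.

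**The case against.** A reader might infer that autoimmune disease is left wholly unbalanced and unchecked. The protocol does not support that.
- The drug lists are broad: TNF, interleukin and JAK inhibitors, methotrexate, azathioprine, calcineurin inhibitors and many MS drugs. All three treatment proxies enter the balance check, so treated disease is partly balanced and partly checked.
- The kidney and blood groups hold diagnoses close to two of the seven outcomes, glomerulonephritis and immune thrombocytopenia.
- Hospital, emergency and outpatient counts are PS terms, and comparators must have a healthcare encounter. Both reduce differences in physician contact.
- Clean periods remove prior cases of the same outcome over 365 days for six of the seven. ADEM has only 28 days.
- For acute outcomes, the self-controlled analysis is repeated in the final database.

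All of this stands, and it narrows the point to disease outside the listed drugs and codes. It does not close the gap. Clean periods address the same diagnosis, not other autoimmune disease. The empiric step ranks by frequency and inclusion is optional. The documents do not show whether any autoimmune code would reach the top 25, but a disease group spread over many codes is poorly suited to such a screen. The outcome-specific PS option is for a confounder that suits one outcome and not the others, whereas this one is shared. Section 9.9 acknowledges residual confounding and names several sources, but not this one.

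**Conclusion.** The point holds as a gap in covariate specification. Autoimmune disease is not a pre-specified PS covariate, is captured only indirectly, and is not itself checked for balance, although it bears on at least seven of 20 outcomes.

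The documents establish neither the size nor the direction of any bias. Under moderate assumptions the null rate ratio is about 1.00 to 1.12. A value near 1.3 needs uncaptured disease to be twice as common in one group and to raise risk 10-fold, among people already matched on immunosuppression, steroids, organ disease and utilization. A reader might take that upper figure as the expected distortion, or conclude that the Phase 2 results are invalid. Neither follows, because every input is assumed.

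The effect is small beside the safety-signal threshold in Section 9.3.2 (rate ratio above 3.0 with P below 0.01). It matters more for the Phase 2 objective, which is estimation, and most for chronic outcomes such as MS, where the cohort is the primary analysis. This is a worthwhile, low-cost improvement, not a fatal flaw.

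**What to change.** Add one binary baseline covariate, autoimmune / immune-mediated inflammatory disease, defined by an ICD-10-CM list over the 365-day baseline. Enter it in Section 9.3.3, the PS equation in Section 9.7.2.1, Appendix IV and the standardized-difference table.

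If matching is already complete, as it may be given the planned end of data collection on 31 August 2025 and a final report due on 30 April 2026, two steps suffice:
1. Report the covariate's standardized difference in the matched cohorts.
2. Include it in the Poisson models for the immune-mediated outcomes. Sections 9.7.2.1 and 9.7.2.2 already provide for covariates in the outcome model when imbalance exceeds 0.1. Here it should be included whatever its standardized difference, since 5% against 7% would pass at 0.08 and still give 1.07 to 1.12 under the stronger assumed risks.

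The cost is one code list, plus either a re-run of the match or an extra adjusted model. Re-matching is the heavier route, because one master cohort feeds every Phase 2 analysis. No new data are needed.

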#### Demographic Attributes

- Sex
- Age (categorical); for the purposes of matching the exposed and unexposed cohorts in Phase 2, we will use the following age groups: 6 months–4 years, 5–11 years, 12–17 years, 18–64 years, and ≥ 65 years
- Calendar month of the vaccination date or cohort entry date (categorical)
- Geographic region (categorical)

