### 9.1.2. Cohort Design

Phase 2 will consist of a propensity score-matched cohort study of individuals with and without a recorded dose of the COMIRNATY 2023-2024 Formula, conducted within the ORD. During the accrual period of 11 September 2023 through 31 March 2024, individuals who receive the COMIRNATY vaccine will be classified as exposed, and those with no recorded vaccination with the COMIRNATY 2023-2024 Formula but who have a healthcare encounter will be classified as comparators. Propensity score matching will be performed to address control of potential confounding, with matching to be conducted within age group and calendar periods. Age group will be defined as: 6 months–4 years; 5–11 years; 12–17 years; 18–64 years; and  $\geq 65$  years, while calendar periods will be defined by 14-day increments (e.g., 01 September 2023 to 14 September 2023, 15 September 2023 to 28 September 2023). Alternate calendar periods (e.g., one month) may be empirically explored. Thus, within any given calendar period, comparators within the same age group will be matched without replacement to a COMIRNATY recipient on PS, down to a maximum allowable level of precision in the PS ([Section 9.7.2.1](#)). This will ensure a sufficient pool of comparators for stratified and/or subpopulation analyses ([Sections 9.7.2.3 & 9.7.2.4](#)).

These matched cohorts will be followed for up to one year for occurrence of safety outcomes. For this Phase 2 matched cohort study, the safety outcomes of interest are listed in [Section 9.3.2](#).

090177e1a5be86fe\Approved\Approved On: 19-Mar-2026 15:57 (GMT)

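### Age is defined only in five bands; if the propensity score uses the same bands, age within 18–64 and within 65+ is controlled only indirectly and the balance check cannot see it

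*Protocol*

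**What the plan says.** Section 9.1.2 sets the bands: "Age group will be defined as: 6 months–4 years; 5–11 years; 12–17 years; 18–64 years", and 65 and over. It plans "matching to be conducted within age group and calendar periods". Section 9.2.3 repeats the bands, introduced there as examples. The covariate list in Section 9.3.3 has the entry "Age (categorical); for the purposes of matching the exposed and unexposed cohorts in Phase 2, we will use the following age groups", followed by the same five bands, and the section states: "Unless specified as for descriptive purposes only, the covariates listed will be included in the PS models".

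The PS formula in Section 9.7.2.1 has one categorical age term (coefficient β2) and gives no cut-points for it. The counts of hospitalizations, emergency visits and outpatient encounters enter as continuous terms. Matching on the PS takes place within "strata defined by age group and calendar period".

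On balance, Section 9.7.2.1 says that "standardized differences between the PS-matched cohorts for each covariate in the model will also be assessed", and adds: "Variables with an absolute standardized difference less than 0.1 will be considered balanced". Section 9.7.2.2 brings covariates into the Poisson model only where the standardized differences show an imbalance.

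Section 7 calls the document a combined protocol and SAP, and Annex 1 lists no standalone documents. According to Section 5, version 3.0 was amended to specify the form of each covariate. The form of age is therefore something this document sets out to fix.

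**The concern.** A five-band age term adds nothing to a match that is already exact on those five bands. An 18-year-old and a 64-year-old in the same calendar period can be matched if their PS values agree, and age itself does not separate those values. Several Phase 2 outcomes depend strongly on age: myocardial infarction, stroke, pulmonary embolism and herpes zoster. If vaccinees and comparators differ in mean age within a band, part of that difference passes into the rate ratio. The planned safeguard would report age as balanced throughout.

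The subgroup aged 65 and over (Section 9.7.2.4) is exactly one matching band. Using the PS as a covariate there gives no direct age adjustment either.

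**Working it through.** The plan states no figure on this point, so there is nothing to reproduce. The first step is logic; the rest is illustration on assumed inputs.

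**1. What the check can see.** Within a stratum, every exposed person and every matched comparator has the same band. With matching-ratio weights, the band proportions agree between cohorts, so the standardized difference for banded age is 0 by construction. Continuous age is not in the model, so it is not among the variables checked. The optional interactions in Section 9.7.2.1, with calendar month or empiric variables, add no finer age.

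**2. The gap that would breach the plan's own 0.1 limit.** Assume comparator age is uniform within the band. The standard deviation is then width/√12.
- 18 to 65: 47/√12 = 13.6 years, so 0.1 corresponds to about 1.4 years.
- 65 to 90 (upper end assumed): 25/√12 = 7.2 years, so 0.1 corresponds to about 0.7 years.

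**3. Rate ratio from a given gap, true value 1.** Let the rate be proportional to exp(k × age), with k = ln 2/10 = 0.0693 for doubling per decade. The spurious rate ratio is the mean of exp(k × age) in the exposed divided by that in the comparators. Exposed age is an exponential tilt of the uniform distribution.

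| Band | Mean gap (years) | Standardized difference, continuous age | Spurious rate ratio |
|---|---|---|---|
| 18–64 | 1 / 2 / 3 / 5 | 0.07 / 0.15 / 0.22 / 0.38 | 1.06 / 1.12 / 1.19 / 1.32 |
| 65+ | 1 / 2 / 3 / 5 | 0.14 / 0.28 / 0.43 / 0.75 | 1.07 / 1.14 / 1.21 / 1.35 |

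For a 5-year gap in 18–64, the rate ratio runs from 1.22 (doubling every 15 years) to 1.41 (every 7 years).

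**4. Crude simulation, 18–64, no covariates.** Logit uptake = −2.6 + b(age − 41), with b = 0.01, 0.02, 0.03. The age gaps are 1.85, 3.66 and 5.37 years. The null rate ratios are 1.11, 1.23 and 1.35 with doubling per decade, and 1.07, 1.15 and 1.22 with a 1.5-fold rise per decade.

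**5. Simulation with indirect control, 18–64.** Here 400,000 people had five age-correlated comorbidities and outpatient visits in the PS, and rates doubled per decade. Comparators were weighted by PS/(1 − PS) in place of matching.

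| Age slope in uptake | Crude gap (years) | Residual gap (years) | Standardized difference | Null rate ratio |
|---|---|---|---|---|
| 0.01 | 2.9 | 1.42 | 0.11 | 1.07 |
| 0.02 | 4.7 | 2.90 | 0.22 | 1.14 |
| 0.03 | 6.3 | 4.15 | 0.31 | 1.20 |

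The covariates removed 51%, 38% and 34% of the crude gap (for example, 1 − 1.42/2.9 = 0.51). With age in years added to the PS, the residual gap was 0.0 years and the null rate ratio 1.00 in all three rows.

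**The case against.** The strongest objection is textual. Section 9.3.3 ties the bands to matching, and the PS formula says only that age is categorical. A term identical to the matching strata would do nothing within them, which is some reason to suppose that finer categories were meant. This stands as a limit on certainty: the identity of the two sets is an inference. But no other categories appear anywhere, and if finer ones are intended, the protocol needs to state them.

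A reader might infer that age within bands is uncontrolled. The document does not support that. The PS also contains comorbidities, three utilization counts, influenza and RSV vaccination and four drug classes, and empiric covariates may be added. Many of these plausibly track age. The simulation in step 5 includes only some of them, so its residual gaps may be too large.

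A reader might also infer bias toward apparent vaccine harm. That is not supported either. Comparators must have a vaccine code or an outpatient encounter (Section 9.3.1.2), which may raise their age. The within-band gap could then shrink or reverse, and a reversed gap would hide harm.

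Finally, the clean return to 1.00 in step 5 used weights, not the greedy digit match that relaxes to a 0.1 caliper. How fully the planned matching would remove the gap has not been shown.

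**Conclusion.** The point holds conditionally. If the PS uses the five bands, within-band age has only indirect control, and a gap above the plan's own limit would go unseen and unremedied. The limitations in Section 9.9 mention residual confounding in general but not this source.

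The size is unknown. In 18–64 with doubling per decade, the illustration gives about 1.07 to 1.20 after partial indirect control, and up to 1.35 with none. These figures rest on assumed age distributions, uptake slopes and rate gradients, none of which the document supplies.

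The consequence is bounded. Errors of this size would not alone meet the signal rule in Section 9.3.2 (rate ratio above 3.0 with P below 0.01). The self-controlled analysis compares each person with themselves over a few months and is unaffected. What is exposed is the Phase 2 estimation of strongly age-dependent outcomes. The change should be made, but the design does not fail without it.

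**What to change.** Keep the five bands as exact-match strata. In Sections 9.3.3 and 9.7.2.1, enter age in years in the PS model (for example as a restricted cubic spline) or in narrow bands with stated cut-points. Report the standardized difference for continuous age overall and within 18–64 and 65+. If any exceeds 0.1, include continuous age in the Poisson model under the existing rule in Section 9.7.2.2.

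No new data are needed, since a missing month and year of birth is already an exclusion. The cost is refitting the PS and re-matching. The milestones put the end of data collection at 31 August 2025 and the final report at 30 April 2026, so matching may already be done. In that case, the continuous-age balance check with outcome-model adjustment can be used without re-matching.
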